14. STATISTICS

14.1. Statistical Plan

A complete description of analysis populations and statistical methods will be provided in a formal Statistical Analysis Plan that will be finalized prior to unblinding and statistical analysis.

Analysis populations

- All Patients Population: Any participant with any record in the database. This
 population includes both screening and randomized subjects. Population will be
 utilized for descriptive patient counts that include screening subjects.
- Intent-to-Treat (ITT) population: All participants randomized to treatment.
- Modified Intent-to-Treat (mITT) Population: All randomized subjects with at least one post-baseline efficacy evaluation will be included in the mITT population and will be analyzed as randomized. The mITT population will be analyzed for efficacy evaluations.
- Per Protocol (PP) Population: For programming purposes, they will be identified as having no major protocol violations as identified separately by the study team and the Sponsor prior to database lock. Analyses of the PP population will be analyzed as treated.
- Safety population: All participants who receive at least 1 dose of drug or placebo.

Demographic data will be presented using descriptive statistics (e.g., mean, standard deviation, median, and range). Exposure to study drug and reasons for discontinuation will be tabulated. Safety analyses will use the Safety population. Safety variables will be tabulated and presented for all subjects who receive study drug or placebo capsules. Adverse events will be coded using the Medical Dictionary for Regulatory Activities (MedDRA). The incidence of treatment-emergent AEs will be presented by system organ class and preferred term. Adverse events will be presented by severity and relationship to study drug. Changes from Baseline in clinical laboratory parameters and vital signs will be summarized across time. Shift tables will be provided for selected laboratory parameters. Physical examination results will be presented in listings.

Primary, secondary and exploratory efficacy analyses of the 11-month on-treatment period will use the mITT population and the per-protocol population unless otherwise specified.

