15. ADVERSE EVENTS

All subjects in the study will have FRDA and the Investigators will take the subjects' Baseline status into account when reporting AEs. Investigators will also consider the underlying disease when designating relationship of AE to study drug, and if AEs are due to the FRDA disease, disease progression or symptomatology exacerbation. Common characteristics of FRDA and RT001 treatment include the following:

- loss of coordination (ataxia) in the arms and legs
- loss of mobility
- fatigue energy deprivation and muscle loss
- vision impairment, hearing loss, and slurred speech
- severe scoliosis
- foot deformities such as clubfoot, flexion of the toes, hammer toes, foot inversion
- diabetes mellitus (insulin-dependent, in most cases)
- hypertrophic cardiomyopathy
- chest pain, shortness of breath, and heart palpitations
- myocardial fibrosis
- heart rhythm abnormalities
- steatorrhea, diarrhea, loose stools

All adverse physical findings/laboratory results identified prior to initiation of study drug will be reported on the medical history and/or physical examination CRFs. After initiation of study drug, any clinically significant changes in physical findings/laboratory results or any new adverse physical findings/laboratory results will be reported as AEs.

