15.2. Adverse Event Classification

15.2.1. Relationship to Investigational Drug

The Investigator's assessment of causality must be provided for all AEs (serious and non-serious). An Investigator's causality assessment is the determination of whether or not there exists a reasonable possibility that the study drug caused or contributed to an AE, as described below:

- None: No relationship between the experience and the administration of study drug; related to other etiologies such as concomitant medications or subject's clinical state.
- Unlikely: The current state of knowledge indicates that a relationship is unlikely.
- **Possible:** A reaction that follows a plausible temporal sequence from administration of the study drug and follows a known response pattern to the suspected study drug. The reaction might have been produced by the subject's clinical state or other modes of therapy administered to the subject, but this is not known for sure.
- **Probable:** A reaction that follows a plausible temporal sequence from administration of the study drug and follows a known response pattern to the suspected study drug. The reaction cannot be reasonably explained by the known characteristics of the subject's clinical state or other modes of therapy administered to the subject.
- **Definite:** A reaction that follows a plausible temporal sequence from administration of the study drug and follows a known response pattern to the suspected study drug and can be confirmed with a positive re-challenge test or supporting laboratory data.

As this is a blinded study, it is assumed the event is related to the active study drug until proven otherwise.

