15.6.2. Reporting to Regulatory Agencies and Institutional Review Boards

If there is a serious and unexpected suspected adverse reaction, the Sponsor will notify the appropriate regulatory agency and all appropriate parties on an expedited basis. In addition, Sponsor must submit expedited reports of an increased rate of occurrence of serious suspected adverse reactions over that listed in the protocol or Investigator Brochure (§ 312.32(c)(1))(iv)).

It is the responsibility of the Investigator to promptly notify the Institutional Review Board (IRB) of all serious and unexpected suspected adverse reactions involving risk to human subjects. Provide a copy of this communication to the Sponsor.

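### Section 15.2.1 presumes that the event, rather than the treatment, is drug-related because the study is blinded, so an event judged Unlikely can be filed as related or unrelated

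*Combined protocol and SAP*

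**What the plan says.** Section 15.2.1 makes causality grading universal: "The Investigator's assessment of causality must be provided for all AEs (serious and non-serious"). The test is a "determination of whether or not there exists a reasonable possibility that the study drug caused or contributed to an AE". Five grades follow: None, Unlikely, Possible, Probable and Definite. None is worded as "No relationship between the experience and the administration of study drug", with the event put down to another cause. Unlikely is a judgement on present knowledge. The section then ends by saying that, because the study is blinded, "it is assumed the event is related to the active study drug until proven otherwise".

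Other places that bear on relatedness:

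- Section 15.1.2 says that, for IND safety reporting, a reasonable possibility requires evidence pointing to a causal link.
- Section 15: "Investigators will also consider the underlying disease when designating relationship of AE to study drug".
- Section 15.5 counts definite, probable and possible as related when it sets out which events are followed until resolved or stable. All serious events are followed whatever their grade.
- Section 9.3.2 requires follow-up of subjects withdrawn for a related event, serious or not.
- Section 14.1: "Adverse events will be presented by severity and relationship to study drug".

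**The concern.** Not knowing the assignment, an investigator can sensibly ask what they would conclude if this subject were on RT001. The closing sentence goes further. Its subject is the event, and what it presumes is relatedness. Nothing in the protocol says how that default maps to a grade, what would count as disproof, or whether it yields to the scale.

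Two investigators could therefore treat the same event differently. One judges it Unlikely and files it as unrelated, following the scale and Section 15.5. The other also thinks a link unlikely, sees that nothing has been disproved, and files it as related. What is at stake is the planned table by relationship (Section 14.1), follow-up of non-serious events under Section 15.5, and follow-up after withdrawal for a related event under Section 9.3.2.

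**Working it through.** The plan states no figure that depends on this rule, so the check is textual.

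**Step 1. Each grade against the closing sentence.**

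| Grade | Under the scale and Section 15.5 | Under the closing sentence, read literally | Conflict? |
|---|---|---|---|
| None | Not related | Related by default, but a clear other cause rebuts it | No |
| Unlikely | Not related | Related: a low likelihood is not disproof | Yes |
| Possible, Probable, Definite | Related | Related | No |

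The conflict is confined to Unlikely.

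**Step 2. Burden of proof.** Section 15.2.1 tests for a reasonable possibility, and Section 15.1.2 says, for IND reporting, that this needs evidence in favour of causation. The closing sentence starts from causation and asks for evidence against it. The two run in opposite directions.

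**Step 3. Underlying disease.** Section 15 lists fatigue, loss of mobility and palpitations among the features to bear in mind. An investigator can often judge that such an event is probably due to Friedreich's ataxia, but can seldom show that the drug played no part. The instruction to weigh the disease points to Unlikely, and the closing sentence points to related.

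**Step 4. What happens to the counts.** In one arm, let R be the number of events graded Possible or higher, U the number judged Unlikely, and k the number of those filed as related because of the closing sentence.

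- Related count = R + k, where 0 ≤ k ≤ U.
- If k is the same in both arms, the difference is (R_active + k) − (R_placebo + k) = R_active − R_placebo, which is unchanged.
- The ratio (R_active + k) / (R_placebo + k) moves toward 1 as k grows.
- If k differs between arms because site mix differs by chance, the comparison picks up noise. Up to 10 centers share 60 subjects randomized 1:1 (30 per arm), and randomization is stratified by FARS score, not by site (Section 8.2).

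The documents give neither U nor k, so the size can only be bounded: at most all Unlikely events in each arm.

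**Step 5. Can it be corrected later?** Under Section 15.6.1, on serious events, the Medical Monitor may raise relatedness but not lower it. Over-application of the default is therefore not reversible by that route. Section 14.1 does not say which grades form the related group in tables, or whether the investigator's or the revised grade is shown.

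**The case against.** The best defence is that the sentence has an ordinary, harmless meaning: since the assignment is unknown, assess each event as though the subject were on active drug. Its opening reference to blinding supports this, and so does the rest of the protocol. A required grade for every event, the instruction to weigh the disease, and an upward-only revision would have little purpose if every event were already related. This probably is what was intended. It does not settle the matter, because the words presume relatedness of the event and no other section says that the scale prevails.

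Several stronger conclusions are tempting, and the documents do not support them:

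- **No event could be graded None under blinding, so all events become related.** The presumption can be rebutted. An ankle sprain after a trip has an evident other cause and can be graded None with the blind intact. A related share of 100% in both arms therefore does not follow.
- **The Section 15.4 action trigger would fire.** It needs an event that is unexpected, Grade 3 or higher, and rated probable or definite. A general presumption assigns neither of those ratings.
- **Every serious unlisted event would need expedited reporting.** Section 15.6.2 begins "If there is a serious and unexpected suspected adverse reaction, the Sponsor will notify the appropriate regulatory agency", and Section 15.1.2 defines a suspected reaction by evidence of a causal link. A default adopted because of blinding is not such evidence.
- **The relationship tables would be unreadable.** A grade exists for every event and can be shown at five levels. Incidence by system organ class and preferred term does not use causality at all.
- **One arm would be favoured.** The same rule applies to both arms under blinding.

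**Conclusion.** The point holds for events judged Unlikely. Followed literally, the closing sentence of Section 15.2.1 puts those events in the related group, while the scale and Section 15.5 leave them out, and nothing in the protocol resolves the conflict. The consequences are related-event counts that are inflated or noisier in both arms and uneven follow-up of non-serious events. The expected direction is dilution of the contrast rather than bias toward one arm.

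This rests on two assumptions: that at least some sites apply the sentence literally, and that some events are judged Unlikely. The documents quantify neither. No efficacy analysis is touched, and the safety tables concerned are descriptive. It is a modest defect that should be corrected because the correction is nearly free.

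**What to change.** Replace the closing sentence of Section 15.2.1 with: *Because the study is blinded, the investigator grades causality on the scale above as if the subject were receiving RT001.* This keeps the presumption about treatment, which blinding justifies, and leaves all five grades usable.

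In Section 14.1 and the analysis plan, state that relationship is tabulated by the grade so assigned, with Possible, Probable and Definite counted as related, as Section 15.5 already does for follow-up.

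The sponsor should note one neighbouring gap that this does not close. Possible, Probable and Definite all require a known response pattern, so a well-timed event of a new kind fits none of them. The present sentence does not close it either, since it assigns no grade.

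The cost is one sentence in Section 15.2.1, one line on tabulation, and matching wording in any site instructions on recording adverse events. The change needs no new data, visits or staff, and can go through the amendment route in Section 17.8. It is best made before further events are graded.

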15.2.2. Severity

All AEs will be graded for severity using the following terms:

Grade 1	Mild	Asymptomatic or mild symptoms; clinical or diagnostic observations only; intervention not indicated
Grade 2	Moderate	Minimal, local or noninvasive intervention indicated; limiting age appropriate instrumental ADL ^a
Grade 3	Severe	Medically significant but not immediately life-threatening; hospitalization or prolongation of hospitalization indicated; disabling; limiting self-care ADL ^b
Grade 4	Life threatening consequences	Urgent intervention indicated
Grade 5	Death	Death related to an AE

^a Instrumental activities of daily life (ADL) refer to preparing meals, shopping for groceries or clothes, using the telephone, managing money, etc.

15.3. Exposure in Utero

The subject will be instructed to notify the Investigator if the subject or subject's partner becomes pregnant during the study. The Investigator must notify the Sponsor within 24 hours via telephone or e-mail and must complete the Pregnancy Notification Form and submit it to the Sponsor within 2 working days of being notified. The Investigator should obtain informed consent/assent from the subject or subject's partner allowing the Investigator to obtain information regarding the pregnancy and its outcome. If the subject or subject's partner provides informed consent/assent, the Investigator should follow the pregnancy until outcome. A final Pregnancy Notification Form should be completed when the outcome of the pregnancy is known.

15.4. Monitoring of Adverse Event Data

The Investigator and the Sponsor or its representative will be responsible for the following:

- Reviewing AE data on an ongoing basis throughout the study. Should any AE report
 suggest that an unexpected Grade 3 or higher, and probably or definite study drugrelated occur, the Investigator and Sponsor will take prompt and appropriate action to
 protect subject safety. These actions may range from no action (proceed with the
 study) to halting the study for safety reasons. The evaluation and action decided upon
 will be documented.
- Assessing the safety data and providing recommendations if the Sponsor should stop or modify the study.

See Section 8.4 for additional details.

^b Self-care activities of daily life refer to bathing, dressing and undressing, feeding self, using the toilet, taking medications, and not bedridden.

15.5. Documentation of Adverse Events by Investigator

Subjects will be evaluated and questioned generally to identify AEs during the course of the study. Any events occurring prior to administration of the first dose will be recorded on the Medical History CRF. Events occurring after administration of the first dose of study drug will be recorded on the Adverse Event CRF. Adverse events that occur up to and including the 90 days after the last dose of study drug must be reported.

Record all AEs spontaneously reported by the subject and/or in response to an open question from study personnel or revealed by observation, physical examination, or other diagnostic procedures on the Adverse Event Form for that visit. Any clinically relevant deterioration in laboratory assessments or other clinical findings is considered an AE and must be recorded on the Adverse Event Form. In addition, an abnormal test finding must be classified as an AE if one or more of the following criteria are met:

- The test finding is accompanied by clinical symptoms.
- The test finding necessitates additional diagnostic evaluation(s) or medical/surgical intervention; including significant additional concomitant drug treatment or other therapy. (Note: simply repeating a test finding, in the absence of any of the other listed criteria, does not constitute an AE.)
- The test finding leads to a change in study drug dosing or discontinuation of subject participation in the clinical research study.
- The test finding is considered an AE by the Investigator.

Wherever possible, a specific disease or syndrome rather than individual associated signs and symptoms should be identified. However, if an observed or reported sign or symptom is not considered a component of a specific disease or syndrome by the Investigator, it should be recorded as a separate AE. Laboratory data are to be collected as stipulated in this protocol. Clinical syndromes associated with laboratory abnormalities are to be recorded as appropriate (e.g., diabetes mellitus rather than hyperglycemia).

For SAEs, a Serious Adverse Event Form must also be completed with as much information as possible and submitted in the time frame described below in Section 15.6. When new significant information is obtained as well as when the outcome of an event become known, the Investigator should record the information on a new Serious Adverse Event Form, indicating that it is a follow-up report. If the subject was hospitalized, a copy of the discharge summary and any other relevant hospital records (e.g., admission report, laboratory test results) must be included as part of the subject medical file.

All AEs considered to be related (definitely, probably, or possibly related) to study drug and all SAEs will be followed until resolved or until a stable status has been achieved.

15.6. Notification about Serious Adverse Events and Serious and Unexpected Suspected Adverse Reactions

15.6.1. Investigator Reporting to Sponsor

All SAEs that occur during the course of the study must be reported by the Investigator to the Sponsor and to the Medical Monitor within 24 hours by telephone or by text message. Additionally, the SAE Form should be faxed/e-mailed within 1 working day from the point in time when the Investigator becomes aware of the SAE. In addition, all SAEs that occur up to and including 90 days after administration of the last dose of study drug must be reported to the Sponsor within 1 working day from when the Investigator becomes aware of the SAE.

Investigators must report to the Sponsor any SAE, whether or not considered drug related, including those listed in the protocol or Investigator Brochure. The report must include an assessment of causality.

For all SAEs, the Investigator is obligated to obtain and provide information to the Sponsor in accordance with the timeframes for reporting specified above. In addition, an Investigator may be requested by the Sponsor to obtain specific additional follow-up information in an expedited fashion. This information may be more detailed than that captured on the Adverse Event eCRF. In general, this will include a description of the AE in sufficient detail to allow for a complete medical assessment of the case and independent determination of possible causality. Information on other possible causes of the event, such as concomitant medications and illnesses must be provided. In the case of a subject death, a summary of available autopsy findings must be submitted as soon as possible to the Sponsor or its designated representative.

The Sponsor's Medical Monitor will review the information submitted and seek further detail if deemed medically relevant and ideally concur on the severity and relatedness. However, the Medical Monitor may revise the severity and relatedness **upward** but may not reduce severity and/or relatedness. Such revisions will be documented in the Sponsor file and provided to the Investigator.

Serious Adverse Event Reporting Contact Information:

[name] Medical Monitor Retrotope, Inc. [name]

[contact] [contact]

15.6.2. Reporting to Regulatory Agencies and Institutional Review Boards

If there is a serious and unexpected suspected adverse reaction, the Sponsor will notify the appropriate regulatory agency and all appropriate parties on an expedited basis. In addition, Sponsor must submit expedited reports of an increased rate of occurrence of serious suspected adverse reactions over that listed in the protocol or Investigator Brochure (§ 312.32(c)(1))(iv)).

It is the responsibility of the Investigator to promptly notify the Institutional Review Board (IRB) of all serious and unexpected suspected adverse reactions involving risk to human subjects. Provide a copy of this communication to the Sponsor.

15.7. Emergency Identification of Study Medication

In the event of a medical emergency, when knowledge of the subject's treatment assignment may influence the subject's clinical care, the Investigator may obtain the treatment assignment of the subject experiencing the emergency through the unblinded statistician/designee. However, prior to unblinding, the Investigator should make every effort to contact the Medical Monitor.

If unblinding is necessary, the Investigator must document the reasons for unblinding in the subject's source documents but should not divulge the subject's treatment assignment to any individuals except the Medical Monitor (if required) and those individuals involved in the direct care of the subject. The date and the reasons for breaking the blind must be submitted to the Sponsor within 24 hours.

If a subject's treatment assignment is unblinded, the subject should remain in the study and continue the protocol-specified follow-up evaluations.

15.8. Optional Sub-Study Adverse Event Monitoring

For the Optional PK Profile Sub-Study, there will be adverse event monitoring because this study will start and stop within the RT001-006 study dosing window.

For the Optional PK Washout Sub-Study, there will not be any adverse event monitoring because the study occurs after the last dose of study drug. SAEs will still be monitored.

